4.2 INFORMED CONSENT PROCEDURES

The consent process will begin via one of two possible pathways:

- 1) Referral of the prospective participant to the investigators/research coordinator by a physician who has knowledge of the proposed research, and obtains patient consent for the research team to approach the patient/surrogate.
- 2) Individuals who have provided signed IRB-approved HIPPA compliant consent for participation in clinical trial research registries.

Subjects must provide informed consent prior to performing any of the study procedures. The information about this study will be given to subjects in language understandable to subjects. Only physician investigators will present the study to the potential subjects. The physician investigator will verbally present a general outline of the research plan, including inclusion and exclusion criteria, to the prospective participant. The consent form, outlining the design of the study, will include the risks and benefits of participating, and will be reviewed and the investigator will answer any questions. Prospective participants may take as much time as required to make an informed decision. Written informed consent will be obtained from each participant prior to performing any research study procedures.

In addition, older potential study participants whose competency to consent is in question will be tested for sufficient comprehension and recall of the information presented. Prospective subjects who do not remember the important facts about participation in the research study after repeated testing will not be included in the study. The investigators will also assess whether a participant understands experimental procedures over time, including assessment throughout the full duration of participation in the study.

5 POTENTIAL RISKS AND BENEFITS

5.1.1 General Risks of Study Protocol and Procedures

The potential subject risks specifically related to the study protocol procedures could include loss of confidentiality or actual physical harm due to experimental intervention as outlined in 5.1.2.

5.1.2 Potential Risks of Experimental Intervention

The potential subject risks specifically related to the study protocol procedures could include:

Venipuncture:

Common Risks: temporary, minor discomfort, bruising.

Other Risks: infection, bleeding and phlebitis.

Belimumab: Common risks are temporary and self-limited or treatable with over the counter (OTC) medication (e.g., Benadryl, Tylenol). The common adverse effects reported with belimumab include nausea, diarrhea, and fever, as well as hypersensitivity and infusion-site reactions. However, there were few differences between treatment and placebo patients in the monitored clinical trials. Infusion reactions were reported in 17% (251/1458) and 15% (99/675) of patients receiving belimumab and placebo, respectively. Serious infusion reactions (excluding hypersensitivity reactions) were reported in 0.5% of belimumab patients and 0.4% of placebo patients.

Serious infection rates were comparable among drug and placebo cohorts (6.0% and 5.2%, respectively). Progressive multifocal leukoencephalopathy (PML) resulting in neurological deficits, including fatal cases, has been reported in SLE patients receiving immunosuppressant pharmacotherapy, including belimumab.

There were 14 deaths during the controlled period of three clinical trials: 3/675 in placebo, 5/673 in belimumab 1 mg/kg; 0/111 in belimumab 4 mg/kg, and 6/674 in belimumab 10 mg/kg. Causes of death included infection, cardiovascular disease, and suicide.

There are no known drug interactions, and the only absolute contraindication is a history of anaphylaxis to belimumab.

5.2 ALTERNATIVE TREATMENTS

The alternative treatments for the subjects participating in this investigation are to continue their usual medical care under the direction of their attending physician.

5.3 POTENTIAL BENEFITS

Participation in the proposed research may or may not provide a direct benefit to the subjects. Potential benefits from the participation in this protocol include enhanced survival, improved respiratory symptoms, and decreased exacerbation frequency and/or severity. Identification of the mechanism(s) mediating these outcomes will facilitate risk-stratification for these adverse outcomes, and development of targeted treatment strategies for the future. Based on the preceding assessment of risks and potential benefits, the risks to subjects are reasonable in relation to anticipated benefits. The research presents a balance of risks and expected direct benefits similar to that available in the clinical setting.

Importance of the Knowledge to be Gained: The preliminary data in this application outline a hypothesis for the development and/or progression of COPD and associated comorbidities. The protocol specifically seeks to address that hypothesis. If the study intervention is found to be both safe and effective in the study population, the treatment of these patients would be altered significantly, and ultimately could lead to a change in the disease natural history. Completion of these protocols will begin to address important questions related to COPD and associated diseases.

5.4 RISK MANAGEMENT PROCEDURES

5.4.1 Protection Against Loss of Confidentiality

All research interventions/activities will be conducted in private patient care areas. The collection of sensitive information about subjects is limited to the amount necessary to achieve the aims of the research, so that no unneeded sensitive information is being collected.

To avoid any violation of subject confidentiality, all data will be stored in a password-protected database as well as Case Report Forms (CRFs), identified only by study ID number. A confidential database linking patient identifying information with study ID number will be maintained by the PIs.

All demographic and clinical information about the subject will be stored in a secured study database under the supervision of the PIs for this protocol. All staff will sign confidentiality statements.

Specimens will be stripped of subject identifiers and stored according to a similar coding protocol as described above. These specimens will be stored safely in the custody of the PIs responsible for the individual assays. These Investigators will limit future access to any remaining sample to only those investigators with prior IRB approval for their studies.

The PIs will retain the data for the entire period of this study. The investigators may continue to use and disclose subjects de-identified information for the purpose of this study for a minimum of seven years after final reporting or publication of the study. If the subject and/or legal representative decide to withdraw or be withdrawn from study participation, they may request that the study data and samples be destroyed.

All staff involved in this study are properly credentialed and instructed in the areas of testing, confidentiality, and safety. All principal and co-investigators, coordinators, and other Key Personnel are required to participate in courses and be certified as mandated by local IRBs regarding human subjects' protections.

5.4.2 Protection Against Risks of Experimental Procedures

Despite the documented safety profile of the study medication in other human disorders of abnormal immune regulation, the study has been designed with a focus on protecting patients against risk including:

Selection of a target patient population with a high risk of morbidity and mortality due to the absence of definitive medical treatment for the disorder

Involvement by trained staff/investigators with experience in the administration of belimumab

Prior human experience with the study medication in other autoimmune disorders, including (SLE).

Selection of a study population that is not taking other immunosuppressive agents will lessen risks of infections.

Continuous monitoring by an independent Data Safety Monitoring Board (DSMB).

Use of low rates of infusions (\geq 1 hour), with continuous monitoring and observations, during study drug administrations. Subjects will be visited and observed by study personnel during each of their treatments. Subjects will also be contacted by phone on the day following their study drug administrations. Assessments for adverse events will occur at each of those contacts.

Infusion reactions occurred more frequently on the first two infusion days and tended to decrease with subsequent infusions. Delay in the onset of acute hypersensitivity reactions has been observed and recurrence of clinically significant reactions after initial resolution of symptoms following appropriate treatment, have been observed. Therefore, patients will be monitored during and for an appropriate period of time after administration of belimumab. Subjects will remain under clinical supervision for 3 hours after completion of the first 2 infusions. Should symptoms of acute hypersensitivity occur, an extended period of monitoring may be appropriate, based on clinical judgement. This may include, but is not limited to, monitoring vital signs and observing any untoward reactions. Beyond the first 2 infusions, subjects will be monitored during and for an appropriate period of time after infusion according to the study sites' guidelines or standard operating procedure for IV infusions. Subjects will be made aware of the potential risk, the signs and symptoms of such reactions, and the importance of immediately seeking medical attention. Delayed-type, non-acute hypersensitivity reactions have also been observed and included symptoms such as rash, nausea, fatigue, myalgia, headache, and facial edema.

Subjects will be made aware of the potential risk, the signs and symptoms of allergic reactions, and the importance of immediately seeking medical attention. In addition, other physicians who have responsible for various aspects of these subjects medical care will have continuous access to study investigators and will be encouraged to immediately report suspected adverse events. Subjects and family members will similarly be encouraged to contact investigators for suspected adverse events. Subjects will be given a wallet-size card explaining that they are in a research study and that they are assigned to receive either belimumab or a matched placebo. The card will include telephone numbers of the responsible investigator. Subjects will be instructed to carry the card at all times.

Some autoimmune diseases have an increased risk of suicidal behavior and/or ideation. For this reason in studies of patients with autoimmune disease, patients will be clinically assessed for suicidal ideation and/or behavior at each visit by experienced medical personnel. It is not known if the increased risk of suicidality with some autoimmune diseases is also present in COPD patients.

PML will be considered in any subject presenting with new-onset or deteriorating neurological signs and symptoms. The subject will be referred to a neurologist or other appropriate specialist for evaluation. If PML is confirmed, the study agent will be discontinued, and the event **will be immediately reported to GSK.**

Medical treatment for conditions that arise as a result of study participation will not be treated by study personnel. The subject will be informed of the problems identified, and this information will be transmitted to the responsible attending physician or physician designated for the subject. In the event of physical injury resulting from the research procedures, medical treatment will be available but not offered free of charge. In addition, financial compensation is not available for wages lost because of injury related to the research protocol. This will be emphasized at the time of consent.

5.5 DATA SAFETY MONITORING PLAN

5.5.1 Data Safety Monitoring Board

A Data and Safety Monitoring Board (DSMB), independent of the study investigators, will monitor the clinical trial outlined in this proposal for the duration of this proposal. The DSMB will be selected by study investigators, in concert and with approval of the sponsor (GSK), from among experts in the field. The Food and Drug Administration has already provided an exemption from IND requirements for this protocol.

The DSMB will be expected to meet as needed, but not less than every six months, to review the progression of the study including patient enrollment, protocol compliance, and adverse event reports. The DSMB will conduct interim monitoring of accumulating data from research activities to assure the continue safety of human subjects, relevance and appropriateness of the study, and the integrity of research data. An emergency meeting of the DSMB may be called at any time by the DSMB Chair should participant safety questions or other unanticipated problems arise.

The UAB study team will assume the following general responsibilities:

- Maintain copies of FWA and Institutional Review Board (IRB) approvals.
- Maintain updated roster of participants.
- Verify eligibility.
- Verify response.
- Collect data on protocol specific CRFs.
- Prepare all submitted data for review by the sponsor and DSMB.
- Maintain documentation of Serious Adverse Event reports and submit these to the sponsor and DSMB for timely review.
- Post on ClinicalTrials.gov

The study PIs will establish a data collection protocol and mechanism. Data will be collected on paper Case Report forms. Numerous data quality checks, such as duplicate entry checks, double-entry verification, and real-time data checking (e.g., ID verification, range checks) will be implemented to ensure that the data are accurate, complete and secure. Data entry personnel will be trained and certified in the correct use of the system.

5.6. ADVERSE EVENTS:

5.6.1. Definition of an Adverse Event:

An adverse event (AE) is any untoward medical occurrence in a patient or clinical investigation subject, temporally associated with the use of a medicinal product, whether or not considered related to the medicinal product.

Note: An AE can therefore be any unfavorable and unintended sign (including an abnormal laboratory finding), symptom, or disease (new or exacerbated) temporally associated with the use of a medicinal product. For marketed medicinal products, this also includes failure to produce expected benefits (i.e., lack of efficacy), abuse or misuse.

Events meeting the definition of an AE include:

- Exacerbation of a chronic or intermittent pre-existing condition including either an increase in frequency and/or intensity of the condition
- New conditions detected or diagnosed after study treatment administration even though it may have been present prior to the start of the study
- Signs, symptoms, or the clinical sequelae of a suspected interaction
- Signs, symptoms, or the clinical sequelae of a suspected overdose of either study treatment or a concomitant medication (overdose per se will not be reported as an AE/SAE) unless this is an intentional overdose taken with possible suicidal/self-harming intent. This should be reported regardless of sequelae

"Lack of efficacy" or "failure of expected pharmacological action" per se will not be reported as an AE or SAE. However, the signs and symptoms and/or clinical sequelae resulting from lack of efficacy will be reported if they fulfill the definition of an AE or SAE

Events that **do not** meet the definition of an AE include:

- Medical or surgical procedure (e.g., endoscopy, appendectomy); the condition that leads to the procedure is an AE
- Situations where an untoward medical occurrence did not occur (social and/or convenience admission to a hospital)
- Anticipated day-to-day fluctuations of pre-existing disease(s) or condition(s) present or detected at the start of the study that do not worsen
- The disease/disorder being studied, or expected progression, signs, or symptoms of the disease/disorder being studied, unless more severe than expected for the subject's condition

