2.7.2. Secondary End-Points

Specific Aim 2 Endpoints: The secondary endpoints of this trial are: 1.) treatment effects on concentrations of pneumococcal polysaccharide-binding antibodies by ELISA^{33,36} 2.) treatment effects on absolute numbers and phenotypes of circulating B-cells by flow cytometry,⁸ and 3.) Adverse event comparisons.

Secondary endpoint #1. (anti-pneumococcal antibodies) and #2. (B-cells) will be assessed among blood specimens obtained prior to treatment, and at 1, 3, 5, and 7 months after treatment starts. Secondary endpoint #3 (AE) will be assessed at each clinic visit, telephone encounter and in communications initiated by subjects or study personnel at any other interval.

a.) Pneumococcal polysaccharide-binding antibody concentrations in plasma will be measured pre-treatment, and compared to results at the aforementioned intervals after treatment started. The ELISA methodology is straightforward, highly standardized, and fully detailed previously.³⁶

b.) B-cell numbers and phenotypes will be assessed at the same time-points. Method-ologies are also well established and have been previously detailed.⁸ In brief, B-cells will be stained with panels of fluorochrome-conjugated monoclonal antibodies and characterized by flow cytometry. B-lymphocytes will be identified as CD3⁻/CD14⁻/CD16⁻/CD19⁺ cells, and further stratified for comparisons as transitional (IgD⁺/CD38⁺⁺), IgM⁺ IgA⁻ IgG⁻ switched memory (IgD⁺/CD27⁺), IgG⁺ switched memory (IgD⁻/CD27^{+/-}), and plasmablasts (CD19^{lo/+}, CD20⁻, CD38⁺⁺, IgD⁻, CD27⁺⁺).⁸

c.) Adverse Events: The NCI Common Toxicity Criteria Scale will be used to define grades (severity) of adverse events and toxicities. An adverse event is defined as any untoward medical occurrence in a subject, regardless of its relationship to these treatments. Toxicity is an adverse event with a direct relationship to the study drug. All toxicities are adverse events, but not all adverse events are toxicities. Case report forms (CRF) will require responses to all adverse events (and negatives), with a particular focus on allergic reactions, infections (including location and organism), and neuropsychiatric symptoms. Recording adverse events in pre-specified checklists (and free text entries) in all subjects will guard against unintended bias.

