- g. All events of possible drug-induced liver injury (see Section 5.6.5) with hyperbilirubinaemia defined as ALT ≥ 3xULN and bilirubin ≥ 2xULN (>35% direct) (or ALT ≥ 3xULN and INR>1.5, termed 'Hy's Law' events (the INR threshold value stated will not apply to patients receiving anticoagulants)

Laboratory and Other Safety Assessment Abnormalities Reported as AEs and SAEs

Any abnormal laboratory test results (hematology, clinical chemistry, or urinalysis) or other safety assessments (e.g., ECGs, radiological scans, vital signs measurements), including those that worsen from baseline, and felt to be clinically significant in the medical and scientific judgement of the investigator are to be recorded as AEs or SAEs. However, any clinically significant safety assessments that are associated with the underlying disease, unless judged by the investigator to be more severe than expected for the subject's condition, are **not** to be reported as AEs or SAEs.

Pregnancy

Any pregnancy that occurs during study participation must be reported to GSK. To ensure subject safety, each pregnancy must be reported within 2 weeks of learning of its occurrence. The pregnancy must be followed up to determine outcome (including premature termination) and status of mother and child. Pregnancy complications and elective terminations for medical reasons must be reported as an AE or SAE. Spontaneous abortions must be reported as an SAE.

Any SAE occurring in association with a pregnancy, brought to the investigator's attention after the subject has completed the study and considered by the investigator as possibly related to the study treatment, must be reported to GSK within 24 hours of learning of its occurrence.

The National Cancer Institute Common Toxicity Criteria Scale will be used to define grades (severity) of adverse events and toxicities. An adverse event is any untoward medical occurrence in a participant who received study drug, regardless of its relationship to the study drug. Toxicity is an adverse event with a direct relationship to the study drug. All toxicities are adverse events, but not all adverse events are toxicities. This is a determination made by the study investigator. The study investigators will classify adverse events as "definitely or most likely," "possibly," or "very unlikely" due to the study drug. Toxicity will be defined as an adverse event that is definitely, most likely, or possibly caused by the study drug.

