Patients who develop acute exacerbations that require an addition to their lung medications, or a hospitalization, will be terminated from the study. Any subject who develops new conditions or statuses that would have been an exclusion criterion, will be terminated from the trial.

Request by the subject to withdraw from the study.

Specific Liver Chemistry Stopping Criteria:

Liver chemistry stopping and increased monitoring criteria have been designed to assure subject safety and evaluate liver event etiology (in alignment with the FDA premarketing clinical liver safety guidance).

- ALT Absolute: $ALT \ge 8x$ upper limit of normal (ULN)
- ALT Increase:
 - \circ ALT \geq 5xULN but <8xULN persists for \geq 2 weeks
 - ALT \ge 3xULN but <5xULN persists for \ge 4 weeks
- Bilirubin: ALT \ge 3xULN and bilirubin \ge 2xULN (>35% direct bilirubin)

All events of ALT \ge 3xULN and bilirubin \ge 2xULN (>35% direct bilirubin) or ALT \ge 3xULN and INR>1.5, if INR measured which may indicate severe liver injury (possible 'Hy's Law'), must be reported as an SAE (excluding studies of hepatic impairment or cirrhosis); INR measurement is not required and the threshold value stated will not apply to subjects receiving anticoagulants.

- INR: ALT \geq 3xULN and INR>1.5, if INR measured
- Cannot Monitor:
 - \circ \quad ALT \geq 5xULN but <8xULN and labs cannot be monitored weekly for $\geq\!\!2$ weeks

- ALT ≥ 3xULN but <5xULN and labs cannot be monitored weekly for ≥4 weeks
- Symptomatic: ALT ≥ 3xULN associated with symptoms (new or worsening) believed to be related to liver injury or hypersensitivity
 - New or worsening symptoms believed to be related to liver injury (such as fatigue, nausea, vomiting, right upper quadrant pain or tenderness, or jaundice) or believed to be related to hypersensitivity (such as fever, rash or eosinophilia)

Required Actions, Monitoring, and Follow up Assessments following ANY Liver Stopping Event Actions:

The study treatment will be Immediately discontinued

The event will be reported to GSK within 24 hours

Liver event follow up assessments will be performed (as stated below)

The subject will be monitored until liver chemistries resolve, stabilize, or return to within baseline (see MONITORING below)

Treatment will not be restarted or rechallenged in the subject

Monitoring:

For bilirubin or INR criteria:

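### The adverse-event definition in 5.6.1 both includes and excludes a COPD exacerbation, so exacerbations that do not lead to hospitalization may be missed or counted inconsistently in the AE comparison

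*Combined protocol and SAP*

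**What the plan says.** Section 5.6.1 lists among events that are AEs: "Exacerbation of a chronic or intermittent pre-existing condition including either an increase in frequency and/or intensity of the condition". Among events that are not AEs it lists "The disease/disorder being studied, or expected progression, signs, or symptoms of the disease/disorder being studied", with the qualifier "unless more severe than expected for the subject's condition". COPD exacerbation is named in neither list.

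The other relevant text is broader:

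- **2.7.2**, which defines the endpoint: "An adverse event is defined as any untoward medical occurrence in a subject, regardless of its relationship to these treatments".
- **5.6.2**, general definition: "An adverse event is any untoward medical occurrence in a participant who received study drug, regardless of its relationship to the study drug". The same section sends all untoward occurrences seen in subjects to the AE case report form.
- **5.6.2**, seriousness criteria: an untoward occurrence that requires hospitalization is serious. The criterion has no exception for the disease studied.
- **5.6.4**: "Patients who develop acute exacerbations that require an addition to their lung medications, or a hospitalization, will be terminated from the study".

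Adverse event comparison is the third secondary endpoint (2.7.2). Section 2.8.2 compares the proportion of subjects with AEs by Fisher's exact test and the count per subject by an exact Poisson test. It does not say whether exacerbations count. The events of special interest in 5.6.3 are serious hypersensitivity or infusion reactions, serious infections, malignancy and suicidality.

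**The concern.** Every subject has COPD, and COPD is the disease under study. An acute exacerbation is therefore a worsening of a chronic pre-existing condition, which is an AE, and also a manifestation of the disease studied, which is not an AE if it was expected. Two people applying 5.6.1 in good faith could classify the same event differently.

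The event is foreseeable. The synopsis calls a past exacerbation the largest risk for another, yet admits subjects with one in the previous 12 months if none fell in the last four. Section 2.9.1 anticipates drop-outs from exacerbations. An event that the protocol foresees is easily called expected, and that is what triggers the exclusion.

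What is at stake is the completeness of the safety comparison. Section 2.9.1 singles out promotion of infection as a concern in this population, and 2.9.2 describes the safety examination as critical. An exacerbation treated without hospitalization is not itself in the special-interest list, and neither of the other two secondary endpoints would capture it. If the AE form omits it, it leaves the AE comparison.

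**Working it through.** The plan gives no figure on this point, so the check is mainly a comparison of texts.

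**Step 1. Does an exacerbation meet both bullets in 5.6.1?** Yes. The including bullet needs a chronic pre-existing condition that increases in frequency or intensity. The excluding bullet needs signs or symptoms of the disease studied that are no more severe than expected. Nothing ranks the bullets or sets a threshold.

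**Step 2. Do other sections settle it?**

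| Section | Effect on a COPD exacerbation |
|---|---|
| 2.7.2, AE definition | AE; no exclusion |
| 5.6.1, including bullet | AE |
| 5.6.1, excluding bullet | Not an AE if expected |
| 5.6.2, general AE definition | AE; no exclusion |
| 5.6.2, recording rule | Goes on the AE form |
| 5.6.2, hospitalization criterion | Serious if hospitalized; no exclusion |
| 2.8.2, analysis | Silent |

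The broad texts conflict with the exclusion, but none says that it overrides it. The exclusion is the more specific text, so a reader could let it prevail.

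**Step 3. Which exacerbations are exposed?** The synopsis calls an exacerbation moderate if treated as an outpatient and severe if it requires hospitalization. Severe ones meet the seriousness criterion, unless a reader first decides under 5.6.1 that they are not AEs. The clear exposure is the remainder.

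**Step 4. Would the question arise?** *Assumption:* a per-subject exacerbation risk r between 10% and 50%, independent across 18 subjects. The documents give no rate.

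- Expected subjects affected, 12r and 6r: 1.2 to 6 on belimumab and 0.6 to 3 on placebo.
- Chance of at least one among 18, 1 − (1 − r)^18: 85% at r = 10%, over 99.9% at r = 50%.

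**Step 5. What could omission do to the AE proportion?**

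- With arms of 12 and 6, two subjects dropped on belimumab (2/12) or one on placebo (1/6) would move that arm's proportion by 16.7 percentage points.
- With the 25 randomized subjects in the synopsis, split about 17 and 8 (*assumption*), the shifts are 2/17 = 11.8 and 1/8 = 12.5 points.
- Each shift is a ceiling. It occurs only if the affected subjects had no other AE; otherwise the proportion does not change. The count per subject falls by the omitted events in either case.

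**Step 6. Could it change the contrast between arms?** *Assumption:* other-AE risk 20% in both arms, exacerbation risk 60% on belimumab and 10% on placebo, independent of each other.

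- Exacerbations counted: 1 − 0.8 × 0.4 = 68% against 1 − 0.8 × 0.9 = 28%. Exact Fisher power with 12 and 6 subjects is 0.28.
- Not counted: 20% against 20%, rejection rate 0.01.
- With an other-AE risk of 50%, the two figures are 0.13 and 0.03.

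Classification can hide a contrast, but the test is weak either way. The loss is chiefly to the description of safety.

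**The case against.** The bullets can be read together: worsening is an AE, while the disease itself and its usual course are not. The note in 5.6.1 counts disease that is new or exacerbated, and the neighbouring exclusion for day-to-day fluctuation is limited to conditions that do not worsen. Sections 2.7.2 and 5.6.2 also call for pre-specified checklists that focus on infections. On this reading every exacerbation already reaches the AE form. The reading is reasonable, but the protocol does not adopt it, and a stated exclusion with an undefined threshold remains.

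Several stronger readings are tempting, and the documents do not support them:

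- *That 5.6.2 repeats the exclusion for all AEs and serious AEs.* The sentence on "any clinically significant safety assessments that are associated with the underlying disease" stands under laboratory and other safety assessment abnormalities. It does not cover clinical events such as exacerbations.
- *That the investigator decides each case.* Only that same sentence names a judge: "unless judged by the investigator to be more severe than expected for the subject's condition". The bullet in 5.6.1 names none.
- *That an exacerbation that ends participation can disappear.* The termination is itself visible, and 5.6.5 has withdrawals reviewed alongside AEs. It is the place in the AE comparison that is uncertain.
- *That the study-wide stopping rule fails.* It compares serious AE rates, and a hospitalized exacerbation meets the seriousness criterion.
- *That the protocol treats exacerbation as its key safety outcome.* Section 2.9.1 singles out infection, not exacerbation.

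The trial is double-blind (2.1), so discretionary coding is unlikely to differ systematically by arm. That answers the concern about differential bias, but not the one about incomplete or inconsistent counts.

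**Conclusion.** The contradiction is real and worth correcting. Section 5.6.1 places a COPD exacerbation on both sides of the AE definition without precedence or threshold, and the broader texts in 2.7.2 and 5.6.2 conflict with the exclusion without clearly overriding it. The practical consequence is that mainly non-hospitalized exacerbations may be under-counted, or counted inconsistently, in secondary endpoint 3. Hospitalized exacerbations are at risk only if the 5.6.1 exclusion is applied before the seriousness test.

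The size cannot be derived from the documents. A reader might take a shift of about 17 percentage points in an arm's AE proportion as the effect. That figure is only a ceiling for the stated example: it assumes arms of 12 and 6 and no other AE in the affected subjects, and the true shift could be zero. The conclusion rests on the wording, not on the illustrative rates.

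**What to change.** Reconcile 2.7.2, 5.6.1 and 5.6.2:

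1. In 5.6.1, state that the exclusion for the disease studied does not apply to COPD exacerbations, and that these are recorded as AEs whether or not they were expected.
2. In 5.6.2, state that an exacerbation that meets a seriousness criterion is a serious AE, with no prior test of expectedness.
3. In 2.7.2 and 2.8.2, refer to that single definition and say that exacerbations count in the AE proportion and in the count per subject.
4. Tabulate exacerbations by arm, split by hospitalization, next to the events of special interest in 5.6.3.

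The synopsis indicates that some subjects have already been withdrawn. The same rule should therefore be applied to existing records, including terminations under 5.6.4, before unblinding.

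The cost is a few sentences, a line on the case report form and somewhat more AE reports. Treatment, visits and sample size do not change.
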